### 2.3.3 ASSESSMENT OF POTENTIAL RISKS AND BENEFITS

As described above, the potential risks of participating in Le Rêve 3.0 relate to potential adverse reactions that may occur in response to CBD or terpenes. However, given the relatively low dose of CBD found in Defined CBD (300 mg or ~3.3 mg/kg/day for a 90 kg male) that will be used in Le Rêve 3.0 relative to that used clinically with Epidiolex® (20 mg/kg/day or 1,800 mg total for a 90 kg male), we anticipate that if AEs are observed, they will occur at a much lower frequency lower than in patients treated with Epidiolex®. Although the potential safety risks in Le Rêve 3.0 are extremely low, the information gained in the study on how CBD may affect sleep physiology may benefit millions of current CBD consumers.

### 3 OBJECTIVES AND ENDPOINTS

OBJECTIVES	ENDPOINTS	JUSTIFICATION FOR ENDPOINTS
Primary		
The primary objective is to determine if Defined CBD influences objective measures of sleep physiology.	The primary endpoint is the percentage of time spent in slow wave (Deep) and REM sleep as quantified by a non-invasive wrist-worn sleep-tracking device called Whoop.	Deep and REM sleep are thought to contribute significantly to restorative sleep. We will use an unbiased approach to collect objective data on these sleep stages to determine if Defined CBD increases deep and REM sleep.
Secondary		
The secondary objective(s) are to determine if Defined CBD influences objective and subjective measures of sleep physiology.	Additional objective secondary outcome measures that will be collected on the Whoop device include: Total sleep time, sleep latency, the number of sleep disturbances, time spent in each sleep stage, and the percentage of time spent in each sleep stage.  A modified version of a clinically validated questionnaire entitled the Participant Global Impression (PGI)  will be used to track subjective measures of sleep physiology. This data will be collected from study participants in the form of a brief five-minute survey that will be completed on their smartphone at the end of each four-week treatment period. This survey measures the perception of the study participants of the effects of treatment.	Although some early clinical studies suggest that CBD might help people with insomnia, no studies have addressed if it influences objective and subjective measures of sleep physiology. Therefore, we will include a number of objective and subjective secondary outcome measures in this study to fill this void in knowledge.

## 4 STUDY DESIGN

### 4.1 OVERALL DESIGN

We hypothesize that Defined CBD, a novel CBD-based formulation in the form of a small orally administered capsule, will increase the percentage of time participants spend in deep (SWS) and REM sleep, as measured by an objective sleep-tracking device called “Whoop”. Our research study, entitled Le Rêve 3.0, is a double-blind, placebo-controlled, randomized, crossover investigational study to determine if Defined CBD, a Custom-Formulated CBD Capsule, influences sleep physiology. This capsule contains no Δ-9-THC. As this study is only designed to evaluate the effects of Defined CBD on the structure and function of sleep physiology, the phase of the trial is not applicable. This trial is not intended to treat, diagnose, prevent, or cure any disease.

The Le Rêve 3.0 study will involve a cross-over design in which study participants will cycle through two independent treatments, each for four weeks (Treatment 1: Placebo; Treatment 2: Defined CBD). The placebo will look, smell and taste the same as the Defined CBD capsule. The study participants will initially be randomized with respect to the treatment arm, and every participant will cycle through both treatment arms. We will use a double-blind design in which the investigator and study participants will both be blinded to the treatments. Baseline data for each participant will be collected for two weeks prior to initiating treatments, as well as for a one-week washout period following each treatment arm. The entire study duration will be 12 weeks (for Schema see section 1.2).

Primary data for Le Rêve will be obtained in a completely unbiased manner from a non-invasive sleep-tracking wrist-worn device called “Whoop” (<https://www.whoop.com>), that electronically collects and transmits sleep data from study participants in the comfort of their own beds.

The wristband collects hundreds of data points per second from a 3-axis accelerometer, 3-axis gyroscope, and heart rate sensor. The wristband can accurately measure the latency to fall asleep, total sleep time, sleep fragmentation, as well as the time spent in each sleep stage [Light, Slow Wave (Deep), Rapid Eye Movement (REM), and Awake]. The device also collects data using photoplethysmography (PPG), a technique that involves measuring blood flow by assessing superficial changes in blood volume. Heart rate, heart rate variability and respiratory rate, can all be derived from PPG data, and all of these metrics are used in Whoop’s sleep detection and staging algorithms. Importantly, two recent publications, published independently from Whoop, show that data on sleep stages collected from the Whoop device are highly accurate and correlate well with polysomnography (PSG), the gold-standard of sleep tracking used in clinical studies conducted in sleep clinics.

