## 1.2 SCHEMA

### 1.3 SCHEDULE OF ACTIVITIES (SOA)

Procedures	Screening Weeks -4 to -1	Enrollment Day 1	Collect Baseline Data Weeks 1-2	Treatment 1 Weeks 3-6	Treatment Washout Week 7	Treatment 2 Weeks 8-11	Treatment Washout Week 12	Post-Treatment Weeks 13-20
Informed consent	X							
Medical history	X							
Randomization				X				
Administer study intervention				X		X		
Adverse event review and evaluation								X

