## 9.2 SAMPLE SIZE DETERMINATION

A total of 100 participants will provide at least 90% power to detect a 15% difference in the percentage of time participants spend in deep and REM sleep, as quantified using the Whoop sleep-tracking device after the four-week treatment phase. The CRO 83Bar will recruit 8,000 potential study participants using social media, will screen approximately 800 study participants via online screening surveys, will contact 440 participants from a call center, and will ultimately enroll 150 qualified study participants. Based on our two previous clinical studies with Defined CBD, we anticipate a maximum dropout rate of 33% in Le Rêve 3.0.

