### 9.4.2 ANALYSIS OF THE PRIMARY EFFICACY ENDPOINT(S)

The primary endpoint that will be analyzed in Le Rêve 3.0 is the percentage of time study participants spend in deep and REM sleep as quantified using wrist-worn sleep-tracking device Whoop. The difference in the mean percentage of sleep spent in deep and REM sleep in participants that received Defined CBD and the placebo control at the end of the two four-week treatment phases will be compared using a 2-sided test with an alpha level at 0.05 to evaluate superiority. The p-value and 95% confidence interval for the estimate of treatment difference in percentages will be estimated and constructed using the above-mentioned method.

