### 9.4.5 BASELINE DESCRIPTIVE STATISTICS

Not applicable.

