#### 10.1.7 CLINICAL MONITORING

Clinical monitoring will be conducted to ensure that the rights and well-being of trial participants are protected, that the reported trial data are accurate, complete, and verifiable, and that the conduct of the trial is in compliance with the currently approved protocol/amendment(s), with International Conference on Harmonisation Good Clinical Practice (ICH GCP), and with applicable regulatory requirement(s).

- Members of the CBD Sleep Study Team will oversee clinical monitoring via daily text (SMS) messages with study participants to ensure compliance and to capture any AEs and SAEs.
- Members of the CBD Sleep Study Team will oversee clinical monitoring by ensuring that sleep-tracking data is being collected on a daily basis throughout the study.

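### Nightly sleep data from the baseline weeks and washout week 7 have no stated role in the analysis, and no check for carryover is planned

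*Combined protocol and SAP*

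**What the plan says.** Section 4.1 states that "Baseline data for each participant will be collected for two weeks prior to initiating treatments", and continues "as well as for a one-week washout period following each treatment arm". The schedule in Section 1.3 puts baseline in weeks 1-2, the first treatment in weeks 3-6, "Treatment Washout Week 7" between the treatments, the second treatment in weeks 8-11 and a final washout in week 12. Section 10.1.7 has the study team ensure that "sleep-tracking data is being collected on a daily basis throughout the study".

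The analysis sections use less. Section 9.4.2 takes "The difference in the mean percentage of sleep spent in deep and REM sleep in participants that received Defined CBD" and placebo, which "at the end of the two four-week treatment phases will be compared using a 2-sided test". Sections 9.1, 9.4.1 and 9.4.3 use the same formula. None of them names the test or mentions baseline, washout, period, sequence or carryover. Section 9.4.5, on baseline descriptive statistics, reads "Not applicable", and Section 9.4.9 on exploratory analyses says the same.

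On attrition, Section 9.2 enrols 150 to obtain 100 and says "we anticipate a maximum dropout rate of 33"%. Section 7.2 does not replace treated participants who withdraw. Section 9.3 defines no efficacy population and gives no rule for a participant with one period only.

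**The concern.** The primary measure is recorded for 14 nights before any treatment and for 7 nights between the treatments, yet the plan does not say what these nights are for. Two things are at stake.

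- **Precision.** A participant who leaves after period 1 contributes only a between-person comparison. That comparison is noisy, and the participant's own baseline sharpens it. With dropout of up to a third, there may be a fair number of such people.
- **Carryover.** If the first treatment still acts in period 2, the usual two-period estimate is biased. The documents give no reason why one week is long enough and plan no display that would reveal a residual. Week 7 is the untreated week between the periods and so the natural place to look.

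**Working it through.** **1. The plan's own figures.** Enrolment reproduces: 100 / (1 - 0.33) = 149.3, hence 150. The power claim for 100 participants cannot be recomputed, because Section 9.2 gives neither a standard deviation nor a within-person correlation. The correlation below is therefore assumed.

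**2. Completers.** Let B be the weeks 1-2 mean and T1, T2 the two period values. With one common slope b, (T1 - bB) - (T2 - bB) = T1 - T2. The baseline cancels, so its gain for a participant with both periods is zero.

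**3. Participants with period 1 only.** Take each of B, T1 and T2 to have variance 1 and any two of them to have correlation r. Assume equal allocation to the two sequences (Section 6.3 gives no ratio), 100 completers and m participants with period 1 only. Information on the treatment effect is:

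- without baseline: 100 / (2(1 - r)) + m/4
- with baseline: 100 / (2(1 - r)) + m / (4(1 - r²))

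| r | m | without | with | gain |
|---|---|---|---|---|
| 0.5 | 25 | 100 + 6.25 = 106.25 | 100 + 8.33 = 108.33 | 2.0% |
| 0.5 | 50 | 100 + 12.5 = 112.5 | 100 + 16.67 = 116.67 | 3.7% |
| 0.8 | 25 | 250 + 6.25 = 256.25 | 250 + 17.36 = 267.36 | 4.3% |
| 0.8 | 50 | 250 + 12.5 = 262.5 | 250 + 34.72 = 284.72 | 8.5% |

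The value m = 50 is the most that 150 - 100 allows. It requires every dropout to leave after giving usable period-1 data. Section 9.2 calls 33% a maximum, and Section 1.3 puts enrolment before the baseline weeks, so some may leave earlier. For r up to 0.8, 8.5% is therefore a ceiling. As r approaches 1 the gain tends to m/400, or 12.5% at m = 50.

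**4. Carryover.** Let t be the treatment effect, p the period effect and c the residual of Defined CBD in period 2 relative to that of placebo.

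- Defined CBD first: T1 - T2 = t - p - c
- Placebo first: T1 - T2 = -t - p
- Half the difference between the sequences: t - c/2

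With c = 0.2t the estimate is 0.90t, and with c = 0.3t it is 0.85t. With c = -0.2t it is 1.10t. These residuals are illustrations; the documents give none.

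**5. How sharp a week-7 check would be.** Assume 50 completers per sequence, two-sided 0.05, 80% power, person variance 1 and independent night variance 1. The multiplier is (1.96 + 0.84) × √(2/50) = 0.56.

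- Unadjusted: week-7 variance 1 + 1/7 = 1.143, so the smallest detectable difference is 0.56 × 1.069 = 0.60 between-person SD.
- Adjusted for baseline: 1.143 - 1/(1 + 1/14) = 0.210, so 0.56 × 0.458 = 0.26.

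With assumed week-to-week drift these rise to as much as 0.72 and 0.42. If the week-7 residual were 20% of the effect, the effect would have to be at least 0.26 / 0.2 = 1.3 between-person SD for the residual to be detected.

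**6. A use to avoid.** Subtracting a separate baseline from each period adds noise. Under the step 5 variances without drift, the variance of T1 - T2 is 2/28 = 0.071. Subtracting weeks 1-2 and week 7 adds 1/14 + 1/7 = 0.214, giving 0.286, four times as much. With assumed drift the ratio is still 1.6 or more.

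**The case against.** The strongest reply is that the crossover already does what a baseline would do: each completer is his or her own control, and a shared baseline adds nothing for the 100 participants on whom the plan is sized. That stands, and it is why the gain is small. The percentages in step 3 also compare with a mixed model that already keeps period-1-only participants, which the plan does not state. Naming the test and giving a rule for incomplete participants matter more than the covariate.

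Several stronger readings are tempting but not supported.

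- *The nights are excluded from the analysis.* The test is unnamed and Section 9.4.5 concerns descriptive statistics, so the text supports only that no role is stated. In the earlier studies (Section 4.2) the global impression survey was rated against the baseline period, but that is perception, not use of the recorded nights.
- *The precision is substantial.* If sleep drifts from week to week, using baseline and week 7 together could cut the variance of completers' four-week contrasts by up to about 17%. With 50 period-1-only participants, baseline with a slope differing by period could cut total variance by 22% to 29% against completers alone. Both rest on drift variances that the documents do not give, and the common-slope model proposed here would not deliver them. The first also puts week 7 in the model. Week 7 follows treatment, so adjusting for it could bias the estimate if carryover exists. If the outcome is the last week of each phase, the joint gain is at most 3.4%.
- *Carryover always dilutes the effect.* This holds only for a residual in the same direction; a rebound would inflate the estimate.
- *Week 7 is the only possible check.* Early period-2 nights, period sums by sequence and week 12 are also recorded. Week 7 is the one untreated window between the periods.

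**Conclusion.** The point holds as a minor improvement. Baseline and week-7 nights are recorded daily, have no stated role in Section 9, and no carryover check is planned. Using baseline as a covariate would add about 2% to 8% information, mainly from participants with period 1 only. That range assumes 25 to 50 such participants, a correlation of 0.5 to 0.8 and equal sequences, and its top is a ceiling. Nothing in the documents shows that carryover occurs. If it does, the estimate moves by half the residual, in a direction that depends on the residual's sign, and the plan as written would not reveal it. A week-7 display would make a large residual visible but could miss a modest one.

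**What to change.** In Section 9.4.2:

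- Name a mixed model with participant (random), period and treatment, and the weeks 1-2 mean of the same measure as a covariate.
- Keep participants who have period 1 only.
- State whether the outcome is the mean over the whole treatment period or over its last nights. The present wording, "at the end of the two four-week treatment phases will be compared using a 2-sided test", can be read either way.
- Give the model without the covariate as a sensitivity analysis.

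Report week 7 by sequence, adjusted for or as a difference from weeks 1-2, with a 95% CI. Label it a supportive carryover display only. It should not be a covariate in the primary model or a pre-test that selects the analysis, and it should carry a note that a null result does not rule out carryover. Summarise the baseline sleep measures in Section 9.4.5.

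The cost is a few sentences in the plan and a little more analysis work. No new data are needed. The wording should be fixed before unblinding, or the choice of covariate and window will not be credible.

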### 4.2 SCIENTIFIC RATIONALE FOR STUDY DESIGN

[figure not shown]
To date, a rigorous, properly-controlled, and well-powered study to determine if CBD influences sleep physiology has simply never been reported in the scientific literature. Defined Research’s Le Rêve 3.0 study is designed to fill this important void in scientific knowledge.

#### Summary Of Data From Previous Clinical Studies With Defined CBD

[figure not shown]
Defined Research recently completed two smaller independent clinical studies to determine the effects of a Defined CBD on the structure and function of sleep physiology. Each of these independent studies were performed as a double-blind, placebo-controlled, randomized, crossover investigational study to determine if Defined CBD influences sleep physiology in humans. These in-house studies were performed under informed consent, but did not go through the IRB approval process.

After more careful scrutiny of the clinical data from Le Rêve 1.0, we determined that of the participants who responded to treatment with Defined CBD, 9/11 exhibited insomnia or subthreshold insomnia as defined by a clinically validated insomnia severity index [the Pittsburgh Sleep Quality Index (PSQI)] that was completed prior to the clinical study being conducted. After taking Defined CBD, participants who scored as having moderate insomnia in the PSQI exhibited an increase in the percentage of restorative sleep that narrowly missed statistical significance, and a significant increase in the percentage of restorative sleep relative to the placebo control (Fig. 4).

At the end of each treatment period in our clinical studies, participants completed a modified version of a clinically validated questionnaire entitled the Participant Global Impression (PGI). PGI assessments are based on the participant's global perception of the effects of treatment on sleep during each treatment period, as compared to their sleep during the baseline period of the study. Using the PGI assessment, participants perceived that they slept better after taking Defined CBD relative to the placebo control, although this effect did not achieve statistical significance (Fig. 5). Nevertheless, based on post-hoc power analysis we have performed, we believe that this effect would achieve statistical significance with a larger sample number. Importantly, no AEs whatsoever were reported in Le Rêve 1.0.

[figure not shown]

### Summary of Data From Le Rêve 2.0

[figure not shown]
After the successful completion of Le Rêve 1.0, we attempted to replicate this study in an independent cohort of participants. As data from our Le Rêve 1.0 indicated that participants with insomnia most benefitted from treatment with Defined CBD, for Le Rêve 2.0 we only enrolled study those who exhibited moderate or severe insomnia as defined by a clinically validated insomnia severity index (the PSQI).

In Le Rêve 2.0 participants (N = 13) were randomized to take a placebo control or Defined CBD (300 mg CBD, 8 mg terpenes) once daily, one hour before bedtime, for at least four nights per week, for a total treatment period of three weeks.

In pooled data from Le Rêve 2.0, Defined CBD increased the percentage of REM and restorative sleep in participants treated with Defined CBD relative to the placebo control, although only the effect on restorative sleep reached statistical significance (Fig. 6). Similar to Le Rêve 1.0, our second study was not powered to obtain statistical significance, and, as such, we believe that this data represents an encouraging replication of Le Rêve 1.0 in an independent cohort of participants. Moreover, based on post-hoc power analysis we have performed, we believe that the effects of Defined CBD on REM sleep would achieve statistical significance with a larger sample number. As in Le Rêve 1.0, no AEs whatsoever were reported in Le Rêve 2.0.

Our two clinical studies were performed in a decentralized manner in which study participants self-administered treatments and collected sleep data in the comfort of their own homes. We therefore decided to quantify the effects of Defined CBD on sleep physiology when we combined the data from our two small clinical studies. In the combined data set, Defined CBD significantly increased the percentage of time study participants spent in REM and restorative sleep (Fig. 7). The effects of Defined CBD on deep sleep in the combined data set narrowly missed statistical significance (data not shown). As noted previously, based on post-hoc power analysis we have performed, we believe that the effects of Defined CBD on deep sleep would achieve statistical significance in a larger sample number.

#### Conclusions and Clinical Significance Of Research Findings

Our clinical data with Defined CBD indicates that it significantly increases the percentage of time people spend in REM and restorative (deep plus REM sleep), and that these effects are most pronounced in people suffering from insomnia. Importantly, we were able to replicate the effects of Defined CBD on these sleep physiology parameters in two independent participant cohorts. Furthermore, participants who took Defined CBD could also perceive a benefit of the treatment on their sleep quality, and not a single AE was reported in either clinical study.

REM and restorative sleep appear to be critically important for good brain health, and their absence in human populations is often associated with chronic ailments and diseases. For example, REM sleep has an essential role in the process of learning and memory in the hippocampus, and disruption of REM sleep can lead to cognitive impairment and other manifestations. During sleep, the brain is able to repair and grow cells, tissue, and nerves that regenerate and boost the hormone and immune system. Along with good nutrition, exercise and stress reduction, restorative sleep is vital for your optimal physical, mental, and emotional health. Insufficient restorative sleep increases the risk of disorders, such as high blood pressure, diabetes, obesity, stroke and depression. It's also associated with cognitive decline and Alzheimer's disease.

Defined CBD is composed of a novel formulation of CBD and terpenes that we have shown significantly increases REM and restorative sleep in people with insomnia, and these people could correctly perceive the benefit of this treatment (even though they were blinded to the treatments). We would now like to replicate these exciting preliminary findings in a larger participant cohort under IRB approval.

#### 4.3 JUSTIFICATION FOR DOSE

The justification for the route of administration and planned dosage for the Le Rêve 3.0 study is based on published scientific literature and in-house dose range-finding studies completed at Defined Research. In one early but small (N = 10) placebo-controlled clinical study in Brazil, subjects with insomnia that received 160 mg of CBD p.o. reported having slept significantly more than those who had been given a placebo control. More recently, a somewhat larger study in 72 adults with clinically diagnosed anxiety, 25-75 mg/day p.o. CBD improved sleep in 66% of the patients as determined by a sleep quality questionnaire. Unfortunately, this particular study was an open label study (i.e. not blinded), lacked a placebo-control, and did not include any objective measures of sleep physiology. Furthermore, the study was only performed in participants with clinically diagnosed anxiety, adding a further confound. Previous clinical studies with Epidiolex® (which contains 99.9% CBD) indicated that

CBD may cause somnolence and sedation at doses between 10 mg/kg/day-20 mg/kg/day (900-1,800 mg/day for a 90 kg male). In-house dose-ranging pilot studies conducted at Defined Research under informed consent demonstrated that Defined CBD (300 mg p.o.) was well tolerated and significantly increased the percentage of time participants spent in deep and REM sleep (data not shown). These studies formed the basis for the dose of CBD used in Le Rêve 1.0-3.0. As described above, based on a large amount of published clinical evidence, the WHO has established that CBD is non-intoxicating and has an excellent safety profile in humans, and based on previous clinical studies with Epidiolex®9 we anticipate that the dose of Defined CBD that will be used in Le Rêve (300 mg/day) will result in no or minimal AEs.

